Title: Time to Eat Study – Pilot

Investigators: [name] [name] [name] [name] [name] (Study Physician)

1. Abstract:

Growing evidence shows that low-grade chronic inflammation, characterized by elevations in plasma C-reactive protein and particularly Interleukin-6 (IL-6), is an independent risk factor of disability, impaired mobility, and lower walking speed. Low-grade chronic inflammation is a modifiable risk factor. However, it is unknown whether interventions that reduce the levels of inflammatory markers *per se* improve mobility, or avert decline in mobility in older persons.

There also remains an important need for interventions that can improve unhealthy changes in body composition that occur during aging. Given the known loss of lean mass that occurs during both aging and continuous calorie restriction, alternative approaches are needed to help older adults lose unhealthy weight while retaining larger amounts of lean mass. Our recent review suggests that a specific form of intermittent fasting, time restricted feeding, results in weight and fat loss (even when caloric intake is not limited), without significant loss of lean mass. This would be an optimal outcome for overweight, older adults and should also result in a reduction in inflammation and improvement in mobility.

To date, no study has examined the effects of time restricted feeding in older adults. Preliminary data regarding feasibility need to be gathered before a full scale trial can be effectively designed and implemented. Thus, the primary aims of this pilot study are to evaluate the safety and feasibility of time restricted feeding in an older adult population. The Time to Eat Pilot Study will also assess the variance of inflammatory markers, walking speed, physical and cognitive function, grip strength, body measurements, perceived fatigability, and activity level. This allows the refinement of the design, recruitment yields, target population, adherence, retention, and tolerability of a larger scale study.

For this 4-week pilot study, we will recruit 10 overweight, older adults who are at risk for, or with, mobility impairment, as measured by slow gait speed and self-reported mobility difficulty and self-reported sedentary lifestyle to complete. All participants will receive the time restricted feeding intervention, which will consist of fasting for approximately 16 hours per day.

2. Specific Aims:

Growing evidence from our group and others shows that low-grade chronic inflammation, characterized by elevations in plasma C-reactive protein (CRP) and particularly interleukin-6 (IL-6) [1-7] is an independent risk factor for disability, impaired mobility, and slow walking speed [1, 6-11]. Low-grade chronic inflammation is a modifiable risk factor. However, it is unknown whether interventions that reduce the levels of inflammatory markers *per se* improve mobility, or avert decline in mobility in overweight, older persons

Conduct a pilot study of 10 overweight, older sedentary persons at risk for mobility decline to assess:

- (i) Feasibility of the study intervention in the study population
 - a. adherence and retention
 - b. tolerability
 - c. recruitment yields
- (ii) Variance in the following:
 - a. inflammation (IL-6 and CRP) level
 - b. walking speed
 - c. body mass index
 - d. waist circumference
 - e. grip strength
 - f. fatigability level
 - g. activity level
 - h. cognitive functioning as measured by the MoCA
 - i. perceived exertion during the 6 min walk
 - j. health-related quality of life.

3. Background:

Aging is associated with a host of biological changes that contribute to a progressive decline in cognitive and physical function, ultimately leading to a loss of independence, and increased risk of mortality. To date, caloric restriction (i.e., a reduction in caloric intake without malnutrition) is the only non-genetic intervention that has consistently been found to extend both mean and maximal life span across a variety of species [12]. Although attenuated, these effects remain present even when moderate caloric restriction (20-40%) is implemented in middle-age mice [13]. Importantly, prolonged caloric restriction has also been found to delay the onset of age-associated disease conditions such as cancer and diabetes in rodents [14] and in nonhuman primates [15]. Thus, findings from animal studies, including recent primate studies, suggest prolonged caloric restriction has the potential to extend health-span and thereby increase quality of life.

In recent studies conducted in overweight humans, caloric restriction has been shown to improve a number of health outcomes including reducing several cardiac risk factors [16-18], improving insulin-sensitivity [19], and enhancing mitochondrial function [20]. Additionally, prolonged caloric restriction has also been found to reduce oxidative damage to both DNA [21-23] and RNA, as assessed through white blood cells [23]. Thus, findings of initial human clinical trials appear to support the promise of caloric restriction demonstrated in animal studies, at least in overweight adults.

Despite these health promoting biological changes, most individuals have difficulty engaging in caloric restriction over the long-term [24]. Findings from weight loss interventions conducted over the past few decades indicate that the vast majority of individuals who lose weight regain this lost weight over the course of one to five years. An additional concern about implementing calorie restriction in older adults is that the weight loss is comprised of both fat and lean tissue; however, the weight that is frequently regained is primarily comprised of fat. This can lead to a situation where the individuals body composition is worse than when they initiated a weight loss program.

Due to poor long-term compliance and loss of lean tissue that occurs with calorie restriction, there is a need to explore the potential of alternative approaches for reducing body weight, specifically body fat, in overweight older adults. One alternative dietary approach that may produce similar biological changes as caloric restriction that has received increasing interest from the scientific community is Intermittent Fasting. In contrast to traditional caloric restriction paradigms, food is not consumed during designated fasting time periods but is typically not restricted during designated feeding time periods. The length of the fasting time period can also vary but is frequently 12 or more continuous hours.

Evidence that this approach may have beneficial effects on longevity first appeared several decade ago [25]. Since this time, a growing body of literature suggests that fasting periods and intermittent fasting regimens can trigger similar biological pathways as caloric restriction (i.e., increased autophagy and mitochondrial respiratory efficiency), which can result in host of beneficial biological effects including increased circulation and cardiovascular disease protection, modulation of reactive oxygen species and inflammatory cytokines, as well as antimutagenic, antibacterial, and anticarcinogenic effects [26].

We recently completed a review of the literature on the effects of intermittent fasting on changes in body composition in overweight individuals [27]. For the time restricted feeding approach, we identified four clinical trials that measured changes in participant's body composition before and after they received this intervention. An important finding of our review was that participants who engaged in time restricted feeding lost a significant amount of body fat without loss of lean tissue in three of the four clinical trials included in our review. These findings suggest that time restricted feeding results in weight and fat loss (even when caloric intake is not limited) without significant loss of lean mass.

Despite these promising findings, no study to date has examined the effects of time restricted feeding in overweight, older adults. Thus, there is a need to understand

whether a time restricted eating pattern could produce similar beneficial changes on the body composition of older adults, as well as reduce inflammation and improve mobility. Given the known loss of lean mass that occurs during both aging and continuous calorie restriction, time restricted feeding regimens may be an effective approach to help overweight, older adults lose unhealthy weight while retaining larger amounts of lean mass.

To date, no study has examined the effects of time restricted feeding in older adults. Preliminary data regarding feasibility need to be gathered before a full scale trial can be effectively designed and implemented. Thus, the primary aims of this pilot study are to evaluate the safety and feasibility of time restricted feeding in an overweight, older adult population. The Time to Eat Pilot Study will also assess the variance of inflammatory markers, walking speed, physical and cognitive function, grip strength, body measurements, perceived fatigability, and activity level. This allows the refinement of the design, recruitment yields, target population, adherence, retention, and tolerability of a larger scale study.

4. Research Plan:

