4.1 Design

This is a pilot study of 10 overweight, older sedentary persons at risk for mobility decline to assess feasibility of an intermittent fasting intervention program within this study population and evaluate changes in inflammatory level, walk speed, physical and cognitive function, grip strength, body measurements, perceived fatigability, and activity levels.

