4.2 Eligibility Criteria

Inclusion criteria

- Consent to participate in the study
- Men and women \geq 65 years old
- Self-reported difficulty walking 1/4 mile or climbing a flight of stairs
- Self-reported sedentariness (<30 minutes structured exercise per week)
- Walking speed <1 m/sec on the 4 m walk test
- Able to walk unassisted (cane allowed)
- Have a body mass index between 25 40 kg/m² (inclusive)

Exclusion criteria

- Current dietary habits
 - Fasting >12 hours per day
 - Actively trying to lose weight by participating in formal weight loss program or significantly restricting calorie intake
 - Weight loss > 5 lbs in the past month
- Medical history or conditions

- Resting heart rate of >120 beats per minute, systolic blood pressure > 180 mmHg or diastolic blood pressure of > 100 mmHg
- Unstable angina, heart attack or stroke in the past 3 months
- Continuous use of supplemental oxygen to manage a chronic pulmonary condition or heart failure
- Rheumatoid arthritis, Parkinson's disease or currently on dialysis
- o Active treatment for cancer in the past year
- Insulin dependent diabetes mellitus
- Taking medications that preclude fasting for 16 hours (e.g. must be taken with food at least 12 hours apart)
- Any condition that in the opinion of the investigator would impair ability to participate in the trial

Table 1. Schedule of Assessments						
	Phone	Screen/	Week 1	Week 2	Week 3	Week 4
	screen	Baseline	(phone)	(phone)	(phone)	(clinic)
	(phone)	(clinic)				
Verbal consent & phone	Х					
screening						
Consent		X X				
Review of medical		X				
history*						
4 m walk*		X X				
Height*, weight*, waist		Х				X
circumference						
Blood pressure*,		X				X
pulse*, temperature						
6 minute walk		X				Х
Grip strength		Х				X X
Fasting blood collection		Х				Х
Montreal Cognitive		Х				Х
Assessment (MoCA)						
Fatigability		X				X
Questionnaire						
SF-12		X X				X X
Distribute / collect		X				X
accelerometer						
Distribute food intake		Х				
time and sleep diaries						
Review food intake time			Х	Х	Х	Х
diary						
AE review			Х	Х	Х	X X
Satisfaction survey &						X
exit interview						

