4.3 Screening, assessments, and follow-up

* Must be completed to confirm eligibility prior to completing other baseline measurements.

Recruitment and Telephone Screening

Potential participants will be recruited from the general population in the North/Central Florida area through general mailings and advertisements and targeted outreach to those who have consented to participate in the Claude D. Pepper Recruitment Registry (IRB#417-2007).

Potential participants who verbally consent to complete the telephone screening are assessed of the main eligibility criteria, including:

- Age
- Self-reported sedentariness
- Self-reported mobility difficulty
- Self-reported height and weight
- Medical history
- Current dietary pattern

Screening/Baseline Clinic Visit

Those who qualify based on the telephone screening are invited to take part in the in person clinic visit. During this visit, informed consent is obtained and the following assessments are completed:

- Measurement of height and weight to determine body mass index
- 4 m walk test

If the participant is eligible to participate based on these assessments, he/she will then continue with the remainder of the baseline assessments, including:

- Measurement of waist circumference
- 6 minute walk test
- Grip strength test
- Collection of blood sample for the measurement of inflammation biomarkers (IL-6 and CRP)
- Montreal Cognitive Assessment
- Fatigability Questionnaire
- SF-12
- Distribute food intake and sleep time record diaries
- Distribute activity monitor

Weekly Phone Contacts

Participants will be contacted by phone at the end of weeks 1, 2, and 3. The following will be reviewed:

- Time of first and last food or drink consumption over the past week
- Changes in health (adverse events)

Study staff will provide participants counseling if he/she is experiencing difficulty in adhering to the study intervention.

Additional phone calls may be made as needed, if the participant requires additional support or guidance in adhering to the study intervention.

Week 4 Follow-up Clinic Visit

Following 4 weeks of the study intervention, participants will complete a follow-up clinic visit. At this visit, baseline assessments are repeated and participants will be asked to report any changes in health since initiating the study. Additionally, participants will be asked to complete a satisfaction questionnaire and an exit interview about their experience during the study.

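### Section 4.1 promises changes in activity and walk speed, but no activity is recorded before fasting starts and the Week 4 source of walking speed is unclear

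*Combined protocol and SAP*

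**What the plan says.** Aim (ii) in section 2 is headed "Variance in the following" and lists ten measures, among them walking speed (b), activity level (g) and "perceived exertion during the 6 min walk" (i). Section 4.1 goes further than variance. It says the study will "evaluate changes in inflammatory level, walk speed, physical and cognitive function, grip strength, body measurements, perceived fatigability, and activity levels". The stated use is in section 3: "This allows the refinement of the design, recruitment yields, target population, adherence, retention, and tolerability of a larger scale study".

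- **Activity.** The baseline visit list in 4.3 includes the item "Distribute activity monitor", and Table 1 has the monitor distributed or collected at baseline and Week 4. Section 4.5 gives the wear period as the four weeks of the intervention. Section 4.4 starts the fasting ramp-up on Day 1.
- **Walking speed.** Section 4.2 requires "Walking speed <1 m/sec on the 4 m walk test" for entry. Table 1 marks the 4 m walk under Screen/Baseline and shows no Week 4 mark. Section 4.5 has no entry for this test. Section 4.3 says, without listing exceptions, that the baseline tests are done again at Week 4. The 6 minute walk is scheduled at both clinic visits.
- **Exertion.** Apart from the aim itself, no section describes a rating. Section 4.5 presents the 6 minute walk as a distance test.

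**The concern.** A pilot that reports change needs a value from before the intervention and a comparable value during or after it. For activity the first is not planned; for 4 m speed the second may not be. Values that were not collected cannot be recovered at analysis.

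Activity matters because a shift at the start of fasting, in either direction, would bear on how a larger study measures and interprets mobility outcomes. With the planned wear period, such a shift would not be seen. For walking speed, whether paired 4 m values exist would depend on whether staff work from Table 1 or from the text of 4.3. For exertion, staff are given an aim but no instrument, so ratings may be recorded inconsistently or left out.

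**Working it through.** The plan gives no figure to reproduce on this point, so the check is to trace each measure through Table 1 and sections 4.3 to 4.5.

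**Aim (ii) tally.** Seven of the ten measures are scheduled at both clinic visits: inflammation, body mass index, waist, grip, fatigability, MoCA and quality of life. The rest are activity (recorded during the intervention only), walking speed (source unclear at Week 4) and exertion (no scale): 7 + 1 + 1 + 1 = 10.

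**Activity.**

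1. Planned wear days, from 4.4 and 4.5: Days 1-3 (12-14 h), Days 4-6 (14-16 h), Days 7-28 (16 h), so 3 + 3 + 22 = 28. Days before Day 1: 0.
2. Let usual activity be A, and let activity on day t of the intervention be A + s + f(t), where s is the shift when fasting starts and f(t) is any later drift. Change from usual is s + f(t), and it needs an estimate of A. Any contrast within the intervention, such as the mean of Days 7-28 minus the mean of Days 1-6, is a difference in f(t) only, because A and s cancel. The data can therefore show drift and spread, but not s.
3. Could Days 1-3 stand in for A? The exclusion "Fasting >12 hours per day" means entrants habitually fast 12 hours or less, and the first target is 12-14 hours. Only someone already at 12 hours could meet it unchanged. Section 5 expects adjustment to take several days, with energy above or below normal. Days 1-3 are not a neutral reference.
4. The interval between the baseline visit and Day 1 is not stated. Some participants might wear the monitor early, but that would be incidental.

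**Walking speed.**

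1. Under Table 1 the 4 m walk is done at 1 of 2 clinic visits, giving 0 change values. Under a literal reading of 4.3 it is done at 2 of 2, giving up to 10.
2. The Table 1 asterisk ("Must be completed to confirm eligibility prior to completing other baseline measurements") does not settle it. Four rows carry it. Two are marked again at Week 4 (height/weight/waist and blood pressure/pulse/temperature) and two are not (medical history and 4 m walk).
3. The 4 m row shows a doubled X in one cell. Consent, grip strength, SF-12 and AE review also show doubled marks, so this looks like a PDF-reading artefact and not a Week 4 mark.
4. Mean speed can also be had from the 6 minute walk: distance in metres divided by 360 seconds (6 x 60), at both visits.
5. If the 4 m walk is repeated, write the baseline value as T + e1 and the Week 4 value as T + e2, with no true change. Because entry required T + e1 below 1 m/sec, the mean of e1 among entrants is negative and the expected change is positive. The documents give no standard deviation or reliability, so the size of this rise cannot be computed.

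**Exertion.** The wording of the aim ties the rating to the walk, and the walk is scheduled at baseline and Week 4. The time points can be inferred. What is absent is a named scale in 4.3, 4.5 or Table 1.

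**The case against.** The strongest reply on activity is that aim (ii)(g) and the summary in section 3 ask only for variance, that 4.1 does not say change from a pre-intervention level, and that a trend within the intervention is itself a change. It is also true that 0 of 28 follows by definition, since the 28 days are the intervention days. This defeats any inference that aim (ii)(g) cannot be met. It does not remove the gap: a reader of 4.1 will take change in activity, listed beside pre/post measures, to mean change from usual, and the plan cannot supply that.

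On walking speed, a reader might infer that Table 1 and 4.3 flatly contradict each other, or that speed cannot be assessed at Week 4. Neither is supported. The sentence in 4.3 is a loose summary: its baseline list also includes handing out diaries and the monitor, which are plainly not repeated. The two starred rows repeated at Week 4 also hold unstarred items, so the row mark does not prove that every starred test is repeated. Aim (ii)(b) does not name the 4 m test, and the 6 minute walk can supply a speed. What stands is that the plan does not say which test is meant.

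On exertion, a reader might infer that the measure was dropped or has no time point. The documents do not say the first, and the aim's tie to two scheduled walks answers the second. Table 1 lists procedures, not every output (IL-6 and CRP have no rows of their own), so a missing row proves little.

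Finally, this is a descriptive, single-arm pilot of 10, with no test or decision rule resting on these items. That is a reason for low severity, not for leaving the wording as it is.

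**Conclusion.** The point holds, at low severity. The activity gap is a real design gap: as planned, change from usual activity cannot be estimated, while on-intervention variance and trend can. The walking-speed gap is smaller: there are 0 or up to 10 changes in 4 m speed depending on which part of the plan is followed, and an alternative source of speed exists at both visits. The exertion gap is a clarification only.

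This rests on two assumptions: that monitor wear follows 4.5 as written, and that the Table 1 marks were read correctly. The second is uncertain enough that the table should be checked against the original. The counts assume all 10 participants complete both visits.

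It would go too far to conclude that the pilot's main purpose is compromised. Safety and feasibility do not depend on these three measures.

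**What to change.** 1. **Activity.** Have participants wear the monitor they already receive at the baseline visit for a short, stated period before Day 1, and add this to 4.3, 4.5 and Table 1. The cost is a few days' delay before Day 1. Alternatively, narrow 4.1 to activity during the intervention, which costs nothing. With no control group, any change from the earlier period would still be descriptive.
2. **Walking speed.** Check Table 1 against the original. Then either mark the 4 m walk at Week 4 and list it in 4.5, or state that walking speed is taken from the 6 minute walk. The first costs one short test at a planned visit, and the report should note the expected regression to the mean from the entry screen. The second costs one sentence.
3. **Exertion.** Name the scale, record it at both 6 minute walks and describe it in 4.5, or delete aim (ii)(i). The cost is one rating at two planned visits, or none.

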4.1 Design

This is a pilot study of 10 overweight, older sedentary persons at risk for mobility decline to assess feasibility of an intermittent fasting intervention program within this study population and evaluate changes in inflammatory level, walk speed, physical and cognitive function, grip strength, body measurements, perceived fatigability, and activity levels.

4.2 Eligibility Criteria

Inclusion criteria

- Consent to participate in the study
- Men and women \geq 65 years old
- Self-reported difficulty walking 1/4 mile or climbing a flight of stairs
- Self-reported sedentariness (<30 minutes structured exercise per week)
- Walking speed <1 m/sec on the 4 m walk test
- Able to walk unassisted (cane allowed)
- Have a body mass index between 25 40 kg/m² (inclusive)

Exclusion criteria

- Current dietary habits
 - Fasting >12 hours per day
 - Actively trying to lose weight by participating in formal weight loss program or significantly restricting calorie intake
 - Weight loss > 5 lbs in the past month
- Medical history or conditions

- Resting heart rate of >120 beats per minute, systolic blood pressure > 180 mmHg or diastolic blood pressure of > 100 mmHg
- Unstable angina, heart attack or stroke in the past 3 months
- Continuous use of supplemental oxygen to manage a chronic pulmonary condition or heart failure
- Rheumatoid arthritis, Parkinson's disease or currently on dialysis
- o Active treatment for cancer in the past year
- Insulin dependent diabetes mellitus
- Taking medications that preclude fasting for 16 hours (e.g. must be taken with food at least 12 hours apart)
- Any condition that in the opinion of the investigator would impair ability to participate in the trial

Table 1. Schedule of Assessments						
	Phone	Screen/	Week 1	Week 2	Week 3	Week 4
	screen	Baseline	(phone)	(phone)	(phone)	(clinic)
	(phone)	(clinic)				
Verbal consent & phone	Х					
screening						
Consent		X X				
Review of medical		X				
history*						
4 m walk*		X X				
Height*, weight*, waist		Х				X
circumference						
Blood pressure*,		X				X
pulse*, temperature						
6 minute walk		X				Х
Grip strength		Х				X X
Fasting blood collection		Х				Х
Montreal Cognitive		Х				Х
Assessment (MoCA)						
Fatigability		X				X
Questionnaire						
SF-12		X X				X X
Distribute / collect		X				X
accelerometer						
Distribute food intake		Х				
time and sleep diaries						
Review food intake time			Х	Х	Х	Х
diary						
AE review			Х	Х	Х	X X
Satisfaction survey &						X
exit interview						

